7.3.3. Handling of Early Termination Visit Information

In the event that a subject is terminated early from this study on Visit 2, the early termination data for safety variables will be assigned to the closest scheduled time point on Visit 2. If the closest time point has valid data, the early termination data will be assigned to the next available time point.

7.3.4. Pooling of Investigational Sites

The data from all study centers will be pooled together for all planned analyses.

7.3.5. Coding Conventions for Events and Medications

All AEs and medical history will be mapped to the Medical Dictionary for Regulatory Activities (MedDRA Version 23.1) system for reporting (preferred term and body system).

Prior and concomitant medications will be coded using WHO-DD (World Health Organization Drug Dictionary) (Version September 2020, C Format).

7.3.6. Analysis Software

Data manipulation, tabulation of descriptive statistics, calculation of inferential statistics, and graphical representations will be performed primarily using SAS (release 9.4 or higher) for Windows. If the use of other software is warranted, the final CSR will detail what software was used and for what purposes.

7.3.7. Study Data

Study data identified in the schedule for time and events (Table 1) are collected, and source verified, on the electronic data capture (EDC) Datatrak One version 14.6.2.

All study data will be formulated into regulatory-compliant data sets to provide transparency, traceability, and integrity of trial analysis results from the collection source. Observed study data will be mapped to the Clinical Data Interchange Standards Consortium (CDISC) Study Data Tabulation Model (SDTM) and serve as the source data from the trial. All study analyses will be completed using analysis data sets that are derived from the SDTM and follow the CDISC Analysis Data Model (ADaM) architecture.

The methods for programming the CDISC SDTM and ADaM data sets are described in Figure 2.

7.4. Planned Study Analyses

7.4.1. Statistical Summaries: Descriptive and Inferential

Categories for data presentation and analysis will consist of each treatment group: Nyxol + LDP, Nyxol + No Treatment 2 (Nyxol alone), Placebo + LDP, Placebo + No Treatment 2 (Placebo alone).

All statistical tests will be two-sided and a difference resulting in a p-value of less than or equal to 0.05 will be considered statistically significant. The p-values for the analysis of secondary efficacy endpoints and safety endpoints will be considered descriptive. All p-values will be rounded to and displayed in four decimals. If a p-value less than 0.0001 occurs, it will be shown in tables as <0.0001.

Descriptive summaries of variables will be provided where appropriate. For continuous variables, the number of non-missing values (n), mean, standard deviation, median, minimum, and maximum will be tabulated by treatment group. For categorical variables, the counts and proportions of each value will be tabulated by treatment group. Expansion of descriptive table categories within each treatment may occur if such elaborations are thought to be useful.

All study-related data collected will be presented in listings. Study-related data not subject to analysis according to this plan will not appear in any tables or graphs but will be included in the data listings.

7.4.2. Interim Analyses and Data Monitoring

No formal interim analysis or safety monitoring committee is planned for this study.

7.4.3. Final Analysis and Publication of Study Results

The final analysis will be completed after all subjects have completed the study.

7.5. Multiple Testing Procedures

There will be no adjustments for multiplicity and no formal multiple testing procedures are to be implemented with this analysis plan.

7.6. Baseline Values

Baseline values are the values obtained at Visit 1, prior to any treatment administration. If the Visit 1 value is missing, any value collected prior to treatment administration will be treated as the baseline.

8. SUMMARY OF STUDY DATA

8.1. Subject Disposition

A summary of the analysis sets includes the number and percentage of subjects by treatment group and overall for the following categories: subjects in the ARP, subjects in the SP, subjects in the mITT Population, and subjects in the PP Population. All percentages will be based on the number of subjects in the ARP.

End of trial information will also be summarized in this table, including the number of subjects completing the study, the number of subjects who prematurely discontinued the study with reasons for withdrawal, the number of subjects completing the study medication dosing, and the number of subjects who prematurely discontinued the study medication with reasons for study medication discontinuation.

A by-subject data listing of study completion information including the reason for premature study withdrawal, if applicable, will be presented.

8.2. Protocol Deviations

Major protocol deviations, as determined by a Sponsor blinded review of the data prior to database lock and unblinding of the study, may result in the removal of a subject's data from the PP Population. The Sponsor or designee will be responsible for producing the final deviation file; this file will include a description of the protocol deviation and clearly identify whether this violation warrants exclusion from the PP Population. This file will be finalized prior to database lock.

All protocol deviations will be presented in a by-subject data listing, with a flag to indicate if a deviation was considered major and/or exclusionary.

8.3. Demographics and Baseline Characteristics

Subject demographic data and baseline characteristics will be tabulated and summarized descriptively by treatment group and overall. The demographic data and baseline characteristics will be summarized for the mITT Population, PP Population, SP, and ARP. If the mITT population is equivalent to any of the other populations, then only the mITT version will be generated rather than repeating equivalent summaries.

The demographics consist of age (year), sex, race, ethnicity, and study eye, iris color (light blue, dark blue, blue with peripupillary brown, uniform green, green with brown iris ring, central brown and peripheral green, brown with some peripheral green, or brown), and irides type (light or dark). A subject's age in years is calculated using the date of the informed consent and date of birth. Age will be summarized using descriptive statistics. The number and percentage of subjects by sex, race, ethnicity, study eye, iris color, and irides type will also be reported. Percentages will be based on the total number of subjects in the study population presentation.

The following baseline characteristics will be summarized for study eye, fellow eye, and binocular (if applicable), using descriptive statistics:

- BCDVA (photopic and mesopic)
- DCNVA (photopic and mesopic)
- DCIVA (photopic)
- Pupil diameter (photopic and mesopic)
- IOP

All demographic and baseline information will be presented in by-subject listings.

8.4. Medical History

The number and percent of subjects with individual medical histories will be summarized for all subjects by treatment group and overall. Non-ocular and ocular medical history will be summarized separately.

Medical history will be coded using the MedDRA Version 23.1. The number and percentage of subjects with any medical history will be summarized overall and for each system organ class (SOC) and preferred term (PT). Percentages will be calculated based on number of subjects in the SP.

Subject medical history data including specific details will be presented in by-subject listings.

8.5. Prior and Concurrent Medications

The number and percentages of all concomitant medications will be summarized by treatment group, Anatomical Therapeutic Chemical (ATC) level 4, and PT. The total number of concomitant medications and the number and percentages of subjects with at least 1 concomitant medication will be summarized by treatment group. All summaries will be performed using the SP.

A concomitant medication is defined as any medication taken on or after the day of first exposure to study drug.

Prior medications are defined as any medication that has a start and stop date prior to the day of first exposure to any study drug, collected from up to 30 days prior to Screening. The total number of prior medications and the number and percentages of subjects with at least 1 prior medication will be summarized by treatment group.

8.6. Treatment Administration

Treatment administration data for both Treatment 1 and Treatment 2 will be presented in by-subject listings.

9. EFFICACY ANALYSES

Unless otherwise noted, efficacy will be assessed using the mITT and PP populations, with subjects included in their randomized treatment regardless of the treatment they actually received. For the analysis of the primary efficacy endpoint, imputation will be performed for missing data as described in Section 7.3.2.3. Confirmatory analysis of the primary efficacy endpoint may be performed using the ARP, if different from the mITT, also using imputation for missing data. For the analysis of the secondary efficacy endpoints, only observed case data will be used.

All efficacy assessment data, regardless of whether they are included in the analysis, will be presented in by-subject listings.

9.1. Clinical Efficacy

For all efficacy endpoints, Baseline is defined as Visit 1.

All efficacy data will be summarized by treatment group for the Baseline assessment and for Visit 2 timepoints (0 minutes, 30 minutes, 1 hour, 2 hours, 3 hours, 4 hours, and 6 hours), as appropriate.

9.1.1. Primary Efficacy Analysis

The primary efficacy endpoint is the percent of subjects with ≥ 15 letters of improvement in photopic binocular DCNVA on Visit 2 at 1 hour with Nyxol + LDP compared to Placebo alone in the study eye. If the analysis using the PP Population shows a positive effect for Nyxol at the 0.05 level of significance, the primary endpoint will be considered met. The primary efficacy endpoint will be analyzed using a logistic regression model with treatment and light/dark irides as factors and the baseline DCNVA as a covariate. The percentage of subjects in each treatment group meeting the criteria, the odds ratio (OR) with 95% CI, and p-value will be provided. Example SAS code is as follows:

[REDACTED]

By including irides type as a factor in the primary efficacy analysis model, the model efficiency as well as a change in the treatment effect will be increased. Including this factor in the model will also make the results more generalizable to other studies in which the sample characteristics may differ from the current study [2].

In addition, the primary efficacy endpoint will be analyzed by light/dark irides using the same model indicated above but without irides as a factor. For this subgroup analyses, observed case data only will be used; that is, missing values will not be imputed.

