## **9. STATISTICS**

### ***9.1. Sample Size***

A sample size of approximately 140 subjects (40 for Nyxol + LDP and Placebo alone arms and 30 for each of the other 2 arms) who are evaluable for efficacy is needed for the study. The primary treatment comparison will be Nyxol + LDP compared to Placebo alone. Using  $\alpha = 0.05$  significance and a two-tailed test, 76 total subjects (38 subjects each in the Nyxol + LDP and Placebo alone arms) evaluable for efficacy will provide at [REDACTED]  
[REDACTED]  
[REDACTED]

Subjects will be randomized 4:3:3:4 to Nyxol + LDP, Nyxol + No Treatment 2 (Nyxol alone), Placebo + LDP, and Placebo + No Treatment 2 (Placebo alone), respectively.

It is assumed that there will be approximately 7% drop-out between Visit 1 and end of Visit 2. To account for this drop-out, a total of approximately 152 subjects will be randomized into the study.

A diagram outlining treatment arms can be found in [Appendix 5](#).

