### ***12.3. Protocol Deviations/Violations***

The Investigator should not deviate from the requirements of this protocol without prior written approval of the Medical Monitor or Sponsor, except in the event of a medical emergency.

A reportable protocol deviation is defined as nonadherence to the protocol that involves inclusion/exclusion criteria, affects subject safety, rights or welfare, or has the potential to affect the integrity of the data. Examples of major protocol deviations include study enrollment by ineligible subject, loss of key data such as equipment malfunction (e.g., pupillometer), and/or use of a prohibited medication during the study.

All protocol deviations will be reported by entering the event in the appropriate eCRF page. Protocol deviations should be reported to the IRB in accordance with IRB-specific guidelines. If there is any question as to whether the deviation is reportable, Ocuphire or designee and the IRB should be contacted.

All changes to the protocol will be made by the Sponsor or designee as an approved amendment to the protocol, submitted to the FDA, and approved by the IRB prior to implementation.

Changes implemented without prior approval will be considered protocol violations.

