4.2. Study Endpoints

4.2.1. Primary Endpoints

Endpoints will be evaluated following administration of masked Nyxol or Placebo (Treatment 1) at or near bedtime for 3 to 4 days, with administration of LDP or No Treatment (Treatment 2) at the next visit (Visit 2) in the morning. Analysis will be completed for 4 treatment arms:

- Nyxol + LDP
- Nyxol + No Treatment 2 (Nyxol alone)
- Placebo + LDP (LDP alone)
- Placebo + No Treatment 2 (Placebo alone)

The primary efficacy endpoint is the percent of subjects with ≥ 15 letters of improvement in photopic binocular DCNVA on Visit 2 at 1 hour with Nyxol + LDP compared to Placebo alone. The improvement in binocular DCNVA for each subject is relative to the subject's own Baseline value (Visit 1). The analysis of the primary endpoint will be completed for the per-protocol (PP) population, as defined in Section 7.1.2 below.

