5. STUDY METHODS

5.1. General Study Design and Plan

This is a placebo-controlled, double-masked, randomized, 4-arm Phase 2 study in males and females between 40 to 64 years of age with presbyopia. A sample size of approximately 152 subjects will be randomized into 1 of 4 treatment arms with the expectation that approximately 140 subjects will be evaluable for efficacy, where evaluable is defined as having received at least one drop of Treatment 1, administered Treatment 2 (LDP or No Treatment), and completed at least one photopic binocular DCNVA measurement after Treatment 2.

Subjects are evaluated for safety and efficacy following administration of masked Nyxol or Placebo (Treatment 1) at or near bedtime for 3 to 4 days, with administration of LDP or No Treatment (Treatment 2) at the next visit (Visit 2) in the morning. Measurements are made at multiple visits and timepoints, and analysis compares 4 treatment arms:

- Nyxol + LDP
- Nyxol + No Treatment 2 (Nyxol alone)
- Placebo + LDP
- Placebo + No Treatment 2 (Placebo alone)

Subjects are randomized 4:3:3:4 into the above groups.

After randomization, masked Treatment 1 study medications (Nyxol or Placebo) is dispensed. Treatment 1 study medication is taken by the subject at or near bedtime (approximately 8PM-10PM) starting the night of Visit 1 (Screening/Baseline) or at the appropriate evening in order for Treatment 1 to be taken daily for 3 to 4 consecutive days immediately prior to Visit 2.

Treatment 2 (LDP or No Treatment) is unmasked and is administered at Visit 2 by a designated, unmasked, Site Staff member, distinct from the Site Staff member recording measurements/assessments.

Treatment 1 (Nyxol or Placebo) is administered to both eyes (OU) by the subject.

Treatment 2 (LDP or No Treatment) is administered OU by the Site Staff.

The study eye is defined as the eye with worse Baseline photopic DCNVA. In the case where both eyes have the same Baseline photopic DCNVA, the study eye will be the right eye (OD). The non-study eye will be the fellow eye. The study eye and fellow eye will both be evaluated at all assessments.

The schedule for assessments and timing of events is presented in Table 1.

Table 1 Visit Schedule

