5.3. Randomization and Masking

A randomization code for allocating subjects to treatment will be prepared by a masked biostatistician not connected with the study. At the initiation of study-related procedures, every subject who is screened is assigned a subject number within numerical order within each site. Once a subject is qualified for the study, the subject is assigned a randomization number in the order provided by the biostatistician.

[figure not shown]
Subjects will be then randomized 4:3:3:4 into 1 of 4 treatment arms:

- Nyxol + LDP
- Nyxol + No Treatment 2 (Nyxol alone)
- Placebo + LDP (LDP alone)
- Placebo + No Treatment 2 (Placebo alone)

Randomization will be stratified 1:1 by iris color (light/dark irides).

A randomization schema for evaluable subjects by investigational treatment (Treatment 1 and Treatment 2) and irides type is described in Figure 1.

Figure 1 **Randomization schema by investigational treatment and irides type**

The Treatment 1 study medications will be masked to Investigators, Site Staff, study subjects, Ocuphire, and all other study personnel involved in the conduct of the study. Only in case of medical emergency or occurrence of SAEs will the randomization code be unmasked by the Medical Monitor and made available to the Investigator, Ocuphire, and/or other personnel involved in the monitoring or conduct of this study.

Treatment 2 (LDP or No Treatment) is unmasked and will be administered on Visit 2 by a designated, unmasked, Site Staff member, distinct from the Site Staff member recording measurements/assessments.

Randomization for both Treatments will occur at Visit 1.

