7.1.2. Per Protocol Population (PP)

The PP population included all subjects in the mITT population who received one drop of Treatment 1 the day prior to Visit 2 and were administered Treatment 2 at Visit 2, had binocular DCNVA and BCDVA in photopic conditions at Baseline (Visit 1) and at Visit 2 time 1 hour, and had no major protocol deviations. The PP population will be used for the primary endpoint analysis and to analyze all efficacy endpoints, with subjects included in their randomized treatment regardless of the treatment they actually received.

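### The primary endpoint is declared met on the Per Protocol analysis alone, a population fixed partly by post-randomisation events and one the planned imputation cannot reach

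*SAP*

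**What the plan says.** Both documents make PP the primary population. SAP 4.2.1 states: "The analysis of the primary endpoint will be completed for the per-protocol (PP) population, as defined in Section 7.1.2 below". Protocol 9.2 and 9.3.5 agree. SAP 9.1.1 turns this into the decision rule: if its "analysis using the PP Population shows a positive effect for Nyxol at the 0.05 level of significance, the primary endpoint will be considered met". No condition on another population is attached.

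Under SAP 7.1.2, PP subjects are mITT subjects who took Treatment 1 the day before Visit 2, were administered Treatment 2, and also "had binocular DCNVA and BCDVA in photopic conditions at Baseline (Visit 1) and at Visit 2 time 1 hour, and had no major protocol deviations". On deviations, SAP 8.2 reads: "Major protocol deviations, as determined by a Sponsor blinded review of the data prior to database lock". Protocol 12.3 gives examples rather than a closed list: "Examples of major protocol deviations include study enrollment by ineligible subject, loss of key data such as equipment malfunction".

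SAP 7.3.2.3 provides imputation for the primary endpoint in mITT and the ARP, and in PP if needed. The trigger is the share of values missing at Visit 2, 1 hour: LOCF at 5% or less, multiple imputation above that. SAP 9 makes the ARP analysis optional.

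The sample size rests on evaluable subjects. In SAP 5.1, "evaluable is defined as having received at least one drop of Treatment 1, administered Treatment 2 (LDP or No Treatment"), plus at least one photopic binocular DCNVA after Treatment 2. Protocol 9.1 bases its power statement on "76 total subjects (38 subjects each in the Nyxol + LDP and Placebo alone arms) evaluable for efficacy".

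**The concern.** This is a superiority comparison, and the analysis that decides it is the one most open to selection after randomisation. Four consequences follow.

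- **Imputation is idle where it matters.** The deciding analysis is complete-case by construction. A PP success alongside a failing mITT analysis would still count as success.
- **Known outcomes can be discarded.** PP also requires 1-hour BCDVA, which the primary endpoint does not use. A subject with an observed primary outcome can be dropped for lacking it.
- **The sample size was set on a wider group.** Evaluable, as the SAP defines it, is close to mITT, and no allowance is made for further PP losses.
- **The exclusion review is not shown to be blind to what matters.** The stated masking of the sponsor covers Treatment 1: "The Treatment 1 study medications will be masked to Investigators, Site Staff, study subjects, Ocuphire". Treatment 2 is unmasked. Every Nyxol + LDP subject is assigned LDP and no Placebo alone subject is, so Treatment 2 separates the two primary arms. Nothing says that it, or the outcome values, are withheld from the review. Protocol 6.2 also leaves to the sponsor whether a subject's later visits enter the efficacy analysis, without saying what the sponsor may see when deciding.

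A separate wording fault sits in the same paragraph of SAP 9.1.1. The endpoint is called binocular and is also placed in the study eye, and success is expressed as an effect of Nyxol although the contrast is Nyxol + LDP against Placebo alone.

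**Working it through.** **The plan's sample size.** 140 / (1 − 0.07) = 150.5, so 151 against the stated 152: reproduced to within rounding. Each primary arm receives 152 × 4/14 = 43.4 subjects, and 43.4 × 0.93 = 40.4, matching the planned 40 evaluable. The power for 38 per arm cannot be reproduced because the rates and power are redacted.

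**Room for PP losses.** 40 − 38 = 2. More than two further PP exclusions in a primary arm take it below the number in the power statement.

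**Imputable values in PP.** Membership requires the 1-hour DCNVA, and imputation is triggered by its absence. Missing 1-hour DCNVA values inside PP = 0 by definition, so the provision for imputing in PP is empty.

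**Outside PP.** The two primary arms together have 152 × 8/14 = 86.9 randomised subjects. If all the planned 7% drop-out lacked a 1-hour value, 86.9 × 0.07 = 6.1 values would be missing in the ARP. The 5% trigger is 86.9 × 0.05 = 4.3, so multiple imputation would apply there. In mITT the number would be lower, because subjects who never reach Treatment 2 are outside it.

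**Illustrative error rates.** Assumptions: equal true response rates in both arms, 43 per arm, unadjusted Wald test on the log odds ratio with 0.5 added to zero cells, two-sided p ≤ 0.05, and 200,000 simulated trials per scenario.

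| Removed before analysis | 20% response | 30% response |
|---|---|---|
| Nobody | 4.3% | 4.7% |
| 7% of both arms, non-selective | 4.3% | 4.7% |
| 7% of active non-responders and 7% of placebo responders | 5.0% | 5.8% |
| 15% of active non-responders only | 5.4% | 6.1% |
| 15% of active non-responders and 15% of placebo responders | 7.8% | 9.8% |

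Counting only results that favour Nyxol + LDP, as the success rule does, the 7%/7% case moves the rate from 2.1% to 3.9% at 20% response, and from 2.4% to about 4.8% at 30%. At a 10% response rate the two-sided figure is 1.7% with nobody removed and 3.3% in the 15%/15% case.

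**Second test.** This uses a pooled z-test with equal true rates of 10–30%. All active-arm exclusions are non-responders and placebo exclusions are random. A fraction d of each arm is removed, so the active-arm PP rate becomes p/(1 − d). The chance of a false positive favouring active is 2.6–3.0% at d = 0, 3.7–3.9% at 7%, 4.1–5.2% at 10% and 4.8–7.0% at 15% (nominal 2.5%).

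**Single tables, Wald test.**
- 11/40 v 4/40: log OR = ln(11 × 36 / (29 × 4)) = 1.228; SE = √(1/11 + 1/29 + 1/4 + 1/36) = 0.635; z = 1.93; p = 0.053.
- 11/39 v 4/40 (one active non-responder removed): log OR = ln(11 × 36 / (28 × 4)) = 1.263; SE = 0.636; z = 1.99; p = 0.047.

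**Single tables, pooled z-test.** 11/40 v 4/40 gives p = 0.045. Adding back three excluded active subjects as non-responders (11/43 v 4/40) gives p = 0.065. Adding three non-responders to both arms (11/43 v 4/43) gives p = 0.047.

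**The case against.** The choice of PP is deliberate and consistent across both documents, and Protocol 9.4 says the focus for efficacy is on observed cases. This is a Phase 2 trial with one post-baseline efficacy visit. Subjects are analysed as randomised, deviations are classified before lock in a review described as blinded, and the mITT analysis is planned, so a conflict between the two would be visible.

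The numbers can also be challenged, and several challenges stand:

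- The simulations start from all randomised subjects. Part of the 7% drop-out never reaches Treatment 2 and is outside mITT too, so the figures do not isolate PP from mITT. The documents give no number for the PP-specific losses, and 15% has no basis in them.
- The only placebo response rate given is 20.0%, for a gain of at least one line in an earlier trial (Protocol 2.2). A three-line rate in those subjects could not be higher. At 10% response the Wald two-sided error stays below 5% in every scenario run. The Wald test is conservative at low rates, though, and the pooled test shows favourable-direction inflation there when all active exclusions are non-responders.
- Whether one exclusion flips the verdict depends on the test: the 11 v 4 table is already significant under the pooled z-test. Neither test is the planned model, which adjusts for irides and baseline DCNVA. Any population is fragile near a threshold.
- The point about the review is inferred from silence. Treatment 2 does not by itself identify an arm, since LDP also goes to Placebo + LDP and no treatment also to Nyxol alone.
- With the power and rates redacted, the cost of falling below 38 cannot be shown.

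None of this lets the mITT result affect the verdict, and visibility of a conflict is not a rule for resolving it.

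**Conclusion.** The concern holds, and it should be fixed. That PP alone decides, that it depends on post-randomisation events including the 1-hour readings, and that imputation has nothing to act on there follow directly from the text with high confidence. The size of the effect is not known. The error rates rest on assumed response rates and assumed selective exclusions, and show what is possible rather than expected. Non-selective loss does essentially no harm, moderate selective loss adds about one percentage point to two-sided error at 20–30% response, and only the extreme case roughly doubles it.

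Moving to mITT reduces the selection without removing it: mITT still requires a first drop and reaching Treatment 2, but neither the 1-hour outcome nor a deviation ruling. The conclusion stands even if the masking of the deviation review is treated only as a missing detail.

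**What to change.** 1. **Deciding population.** In SAP 4.2.1, 7.1 and 9.1.1 and Protocol 9.2 and 9.3.5, let the mITT analysis with the stated imputation determine whether the primary endpoint is met, with PP as supportive. Under the LOCF branch only the 30-minute value can be carried to 1 hour, so state a rule for mITT subjects without it, for example counting them as non-responders. Keep the ARP as a sensitivity analysis, with a stated rule for subjects who have no value after Treatment 2.
2. **Exclusion review.** In SAP 8.2, state that exclusion decisions, including those under Protocol 6.2, are made on a file without Treatment 2 and without post-Treatment-2 VA and PD values, showing only whether each value is present.
3. **Wording.** In SAP 9.1.1, delete the study-eye phrase and define success as a statistically significant difference favouring Nyxol + LDP over Placebo alone.

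The cost is SAP and protocol text, one missing-data rule and a restricted review file. The mITT analysis is already planned, so no new data or subjects are needed. The estimate may be slightly less favourable than in PP.
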